6.1.2 Enrollment

Enrollment of patients to Group A or B will be done after central determination of the MGMT promoter methylation status and if the general and neurological status of the patient remains stable.

Group A: patients with MGMT promoter-unmethylated AA or GBM will be enrolled.

Group B: patients with MGMT promoter-methylated AA or GBM will be enrolled.

Group C: registration and enrollment occur at the same time, when the patient signs the informed consent form.

6.1.3 Initiation of Study Treatment

6.1.3.1 Group A

The first dose of TG02 and first treatment of RT can be started as soon as the patient is enrolled. A maximum of 7 days is allowed between enrollment and initiation of study treatment. Every effort should be made to reduce the time between enrollment and first dose of study treatment.

On days when both TG02 and RT are scheduled, TG02 will be taken approximately 1 hour before RT treatment.

A patient card and a patient diary will be given to each enrolled patient in order to record AE and treatment intake.

6.1.3.2 Group B

The first dose of TG02 (Day -7) can be started as soon as the patient is enrolled. A maximum of 7 days is allowed between enrollment and first dose of TG02. Every effort should be made to reduce the time between enrollment and first dose.

On days when both TG02 and TMZ are scheduled, TG02 will be taken approximately 1 hour before TMZ treatment.

A patient card and a patient diary will be given to each enrolled patient in order to record AE and treatment intake.

6.1.3.3 Group C

A maximum of 7 days is allowed between registration and first dose of TG02.

A patient card and a patient diary will be given to each enrolled patient in order to record AE and treatment intake.

6.2 Study treatment phase

6.2.1 Cycle 1 for Group A

All cycles are 28 days. Cycle 1 is 21 days of RT and a 7-day break. Cycle 2 will begin after completion of combination TG02 and RT treatment, including the 7 day break.

6.2.1.1 Day 1 (prior to first dose of TG02)

- Concomitant medications assessment
- Steroid dose. For corticosteroids, dose, frequency, dates of administration and route of administration must be recorded in the dedicated eCRF.
- Vital signs: blood pressure, pulse, temperature, weight
- Karnofsky Performance Status (KPS) (see Appendix E)
- Hematology: includes hemoglobin, hematocrit, total WBC count with differential (neutrophils and lymphocytes), and platelet count. If the registration hematology panel has been done within 72 h prior to first dose of TG02, it does not need to be repeated.
- Biochemistry: sodium, potassium, chloride, BUN, creatinine, total protein, albumin, AST and/or ALT, total bilirubin, alkaline phosphatase, calcium, magnesium, LDH, glucose, creatinine kinase and phosphate. If the registration biochemistry panel has been done within 72 h prior to first dose of TG02, it does not need to be repeated.
- Coagulation: PT, PTT and INR. If the registration coagulation panel has been done within 72 h prior to first dose of TG02, it does not need to be repeated.
- Optional translational research: 20 mL blood for soluble biomarker assessment
- **Prescription:** TG02 prescription (+ prophylaxis, see section 5.6.2)

6.2.1.2 Every week (Days 8 and 15)

- Concomitant medications assessment
- Steroid dose. For corticosteroids, dose, frequency, dates of administration and route of administration must be recorded in the dedicated eCRF.
- Vital signs: blood pressure, pulse, temperature, weight
- Karnofsky Performance Status (KPS) (see Appendix E)
- Hematology: includes hemoglobin, hematocrit, total WBC count with differential (neutrophils and lymphocytes), and platelet count

- Biochemistry: sodium, potassium, chloride, BUN, creatinine, total protein, albumin, AST and/or ALT, total bilirubin, alkaline phosphatase, calcium, magnesium, LDH, glucose, creatinine kinase and phosphate
- Adverse events assessment (see section 7.3.1)
- TG02 compliance

6.2.2 Cycle 1 for Group B

Cycle 1 is 35 days including a Day -7 and -4 dose of TG02. All subsequent cycles (Cycle 2+) are 28 days.

6.2.2.1 Day -7 (prior to first dose of TG02)

- Concomitant medications assessment
- Steroid dose. For corticosteroids, dose, frequency, dates of administration and route of administration must be recorded in the dedicated eCRF.
- Vital signs: blood pressure, pulse, temperature, weight
- Karnofsky Performance Status (KPS) (see Appendix E)
- Hematology: includes hemoglobin, hematocrit, total WBC count with differential (neutrophils and lymphocytes), and platelet count. If the registration hematology panel has been done within 72 h prior to first dose of TG02, it does not need to be repeated.
- Biochemistry: sodium, potassium, chloride, BUN, creatinine, total protein, albumin, AST and/or ALT, total bilirubin, alkaline phosphatase, calcium, magnesium, LDH, glucose, creatinine kinase and phosphate. If the registration biochemistry panel has been done within 72 h prior to first dose of TG02, it does not need to be repeated.
- Coagulation: PT, PTT and INR. If the registration coagulation panel has been done within 72 h prior to first dose of TG02, it does not need to be repeated.
- Adverse event assessment (see section 7.3.1)
- Optional translational research: 20 mL blood for soluble biomarker assessment
- **Prescription:** TG02 prescription (+ prophylaxis, see section 5.6.2) and TMZ prescription (+ prophylaxis)

6.2.2.2 Every week (Days 1, 8, 15 and 22)

- Concomitant medications assessment
- Steroid dose
- Vital signs: blood pressure, pulse, temperature, weight
- Karnofsky Performance Status (KPS) (see Appendix E)
- Adverse event assessment
- Hematology: includes hemoglobin, hematocrit, total WBC count with differential (neutrophils and lymphocytes), and platelet count
- Biochemistry: sodium, potassium, chloride, BUN, creatinine, total protein, albumin, AST and/or ALT, total bilirubin, alkaline phosphatase, calcium, magnesium, LDH, glucose, creatinine kinase and phosphate
- TG02 compliance
- TMZ compliance

6.2.3 Cycle 1 for Group C

All cycles are 28 days.

6.2.3.1 Day 1: prior to first dose of TG02

- Concomitant medications assessment
- Steroid dose. For corticosteroids, dose, frequency, dates of administration and route of administration must be recorded in the dedicated eCRF.
- Vital signs: blood pressure, pulse, temperature, weight
- Karnofsky Performance Status (KPS) (see Appendix E)
- Hematology: includes hemoglobin, hematocrit, total WBC count with differential (neutrophils and lymphocytes), and platelet count. If the registration hematology panel has been done within 72 h prior to first dose of TG02, it does not need to be repeated.
- Biochemistry: sodium, potassium, chloride, BUN, creatinine, total protein, albumin, AST and/or ALT, total bilirubin, alkaline phosphatase, calcium, magnesium, LDH, glucose, creatinine kinase and phosphate. If the registration biochemistry panel has been done within 72 h prior to first dose of TG02, it does not need to be repeated.
- Coagulation: PT, PTT and INR. If the registration coagulation panel has been done within 72 h prior to first dose of TG02, it does not need to be repeated.
- Adverse events assessment (see section 7.3.1)
- Optional translational research: 20 mL blood for soluble biomarker assessment
- **Prescription:** TG02 prescription (+ prophylaxis, see section 5.6.2)
- Blood sample for Pharmacokinetics (6 mL blood) for patients consented to the PK study just prior to TG02 administration.

6.2.3.2 Every week (Days 8, 15 and 22)

If no SAEs are reported by the patient or ongoing on Day 8, the safety evaluations on Days 15 and 22 can be omitted.

- Concomitant medications assessment
- Steroid dose
- Vital signs: blood pressure, pulse, temperature, weight
- Karnofsky Performance Status (KPS) (see Appendix E)
- Hematology: includes hemoglobin, hematocrit, total WBC count with differential (neutrophils and lymphocytes), and platelet count
- Biochemistry: sodium, potassium, chloride, BUN, creatinine, total protein, albumin, AST and/or ALT, total bilirubin, alkaline phosphatase, calcium, magnesium, LDH, glucose, creatinine kinase and phosphate
- Adverse events assessment
- TG02 compliance
- Cycle 1 D 15 only: blood samples for Pharmacokinetics (6 mL blood each sample) for patients consented to the PK study: pre-dosing, 30 minutes, 1 hour, 2 hours, 4 hours, 8 hours and 24 hours after dosing.

Following table will serve as an example:

PK Sampling Time Point	Window	Activity	
		Breakfast	
Prior to dosing	Prior to dosing	Pre-dose blood draw (6mL)	
	N/A	Dose TG02	
30 min	+/- 5 min	Blood draw (6 mL)	
1 hr	+/- 10 min	Blood draw (6 mL)	
2 hr	+/- 10 min	Blood draw (6 mL)	
4 hr	+/- 30 min	Blood draw (6 mL)	
	N/A	Lunch	
8 hr	+/- 1 hr	Blood draw (6 mL)	
24 hr	+/- 1 hr	Blood draw (6 mL)	

6.2.4 Cycle 2+ until withdrawal criteria are met (for all groups)

After Cycle 1, all cycles are 28 days for all groups. Visits should be performed at D1 of each cycle every 28 days (\pm 3 days). See section 5.4 for withdrawal criteria.

6.2.4.1 Every 28 days (\pm 3 days)

- Concomitant medications assessment
- Steroid dose. For corticosteroids, dose, frequency, dates of administration and route of administration must be recorded in the dedicated eCRF.
- Vital signs: blood pressure, pulse, temperature, weight
- Karnofsky Performance Status (KPS) (see Appendix E)
- Hematology: hemoglobin, hematocrit, total WBC count with differential -neutrophils and lymphocytes-, and platelet count
- Biochemistry: sodium, potassium, chloride, BUN, creatinine, total protein, albumin, AST and/or ALT, total bilirubin, alkaline phosphatase, calcium, magnesium, LDH, glucose, creatinine kinase and phosphate will be measured
- **Group C, WOBCP only:** urine or serum pregnancy test
- Adverse events assessment
- 12-lead ECG, if clinically indicated
- TG02 compliance
- **Cycle 2 only, Group A: RT compliance; Cycle 2+, Group B: TMZ compliance**
- **Prescription:** TG02, TMZ (+ prophylaxis, see Section 5.6 for TG02 prophylaxis)

6.2.4.2 Every 2 cycles (\pm 8 days) until 6 cycles, then every 3 cycles (\pm 8 days)

- Brain Gd-MRI. See Appendix J for detailed MRI sequences. Additional information can be found in the study specific imaging guidelines
- Complete neurological examination (NANO scale, see section 7.2.4)
- **Group A and B ONLY:** Quality of life assessment (modified EORTC QLQ C30/BN20, see Chapter 10 and Appendix F) at start of cycles 3, 5, 7, 10, 13, etc. (every 3 cycles) until disease progression (to coincide with scheduled visit)

6.2.4.3 Optional translational research biology

Optional translational research biology at C3 D1 2 months after TG02 initiation (20 mL blood for biomarkers analysis)

6.3 At study treatment discontinuation (for all groups)

6.3.1 End of study visit for all groups

End of study evaluation should take place within 30 days (\pm 5 days) after the last dose of TG02

- Complete physical examination
- Concomitant medications assessment
- Steroid dose. For corticosteroids, dose, frequency, dates of administration and route of administration must be recorded in the dedicated eCRF.
- Vital signs: blood pressure, pulse, temperature, weight
- Karnofsky Performance Status (KPS) (see Appendix E)
- Hematology: hemoglobin, hematocrit, total WBC count with differential -neutrophils and lymphocytes-, and platelet count
- Biochemistry: sodium, potassium, chloride, BUN, creatinine, total protein, albumin, AST and/or ALT, total bilirubin, alkaline phosphatase, calcium, magnesium, LDH, glucose, creatinine kinase and phosphate
- Coagulation: PT, PTT and INR
- **Group C, WOBCP only:** urine or serum pregnancy test
- Adverse event assessment. When the patient discontinues study treatment, suspected adverse reactions (AEs for which there is a reasonable possibility that the drug caused the AE) that started while on study treatment should be followed for 30 days from the date of the last dose of study drug or until considered chronic/ stable (as judged by the Investigator), whichever comes first. SAEs and serious suspected adverse reactions that are reported after the last dose of study drug but before 30 days after the last dose of study drug should be followed until resolved or considered stable/ chronic (as judged by the Investigator).
- TG02 compliance. All patient diaries should be collected if not done previously
- **Group B ONLY:** TMZ compliance
- Brain Gd-MRI. See Appendix J for detailed MRI sequences. Additional information can be found in the study specific imaging guidelines
- Complete neurological examination (NANO, see section 7.2.4)
- **Groups A and B ONLY:** Quality of life assessment (modified EORTC QLQ C30/BN20, see Chapter 10 and Appendix F)
- Optional translational research: 20 mL blood for biomarkers analysis

6.3.2 Discontinuation due to progressive disease

If study treatment is discontinued because of progressive disease AND a surgical procedure is planned for recurrent or progressive tumor, TG02 should be maintained until the surgery and tissue should be collected, online registered and sent to Department of Neurology, University Hospital Zurich (refer to sections 11.2.1, 14.3 and HBM guidelines provided as a separate document). If possible, a 10-mL plasma sample should be obtained close to the time of surgery

If a surgical procedure is NOT planned, patients with progressive disease will terminate the study treatment (see “end of study visit” below). The therapeutic strategy at progression will be determined by the treating physician at the participating center. Patients will remain in survival follow-up (see section 6.3.3) unless they refuse further data collection.

6.3.3 Follow-up every 3 months (\pm 14 days)

For all groups:

- Survival, irrespective of type of treatment administered or any progression event. (Follow-up can be done by regular visits or phone calls.)
- If progression has not occurred,
 - Brain Gd-MRI (Appendix J)
 - Quality of life assessment (modified EORTC QLQ C30/BN20) Group A & B only

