6.3.3.1 After progression, until death every 3 months (\pm 14 days)

- Survival. (Follow-up can be done by regular visits or phone calls.)
- Quality of life assessment (modified EORTC QLQ C30/BN20) Group A & B only
- Any antitumoral therapy follow-up (Group C only)

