⁶ Sodium, potassium, chloride, BUN, creatinine, total protein, albumin, AST and/or ALT, total bilirubin, alkaline phosphatase, calcium, magnesium, LDH, glucose, creatinine kinase and phosphate will be measured at registration, Cycle 1 Day 1 pre-dose, Cycle 1 Days 8, 15 and 22, on Day 1 of subsequent cycles, and at the end of study visit. If the registration chemistry panel is done within 72 h of pre-dose on Cycle 1 Day 1, it does not need to be repeated.

⁷ PT, PTT, and INR will be measured at registration, Cycle 1 Day 1 pre-dose and at the end of study visit. If the registration coagulation panel has been done within 72 hours of pre-dose on Cycle 1 Day 1, it does not need to be repeated.

⁸ For WOCBP, serum or urine pregnancy test will be conducted within 72 hours prior to the first dose of TG02, D1 of every cycle and at end of study visit.

⁹ If no SAEs are reported by the patient or ongoing on Day 8, the safety evaluations on Days 15 and 22 can be omitted.

¹⁰ Adverse events grading according to CTCAE 5.0

¹¹ TG02 should start within 7 days of registration. TG02 will be taken on days 1, 4, 8, 11, 15, 18, 22 and 25 in all cycles. Skipped doses of TG02 will be noted in the patient study drug diary. See section 5.2.1.3.

¹² ECG should be repeated if medically indicated.

¹³ Baseline brain Gd-MRI must be completed within 14 days of first dose of TG02. For patients with surgery for recurrence, if a 72-hour post-surgery MRI was done and falls within this time window, baseline MRI does not need to be repeated. Brain Gd-MRI will also be every 2 cycles (\pm 8 days) until 6 cycles, then every 3 cycles (\pm 8 days). If treatment is stopped

before progression is observed, brain Gd-MRI should be done every 3 months (\pm 14 days). See Appendix J for detailed MRI sequences. Additional details can be found in the study specific imaging guideline.

¹⁴ See section 7.2.4.

¹⁵ Safety evaluations in Cycles 2+ should be performed at D1 of each cycle (\pm 3 days)

¹⁶ Efficacy evaluations should be performed every 2 cycles (\pm 8 days) until 6 cycles and then every 3 cycles (\pm 8 days)

¹⁷ End of study visit should be performed within 30 days (\pm 5 days) after the last dose of TG02

¹⁸ Optional collection of 20 mL blood samples for future analysis (baseline, C3D1, progression or end of study)

¹⁹ Follow-up for survival every 3 months (\pm 14 days) and new anti-tumoral therapy information until death. Follow up can be done by regular visits or phone calls.

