Neurologic progression free survival (NPFS): NPFS is defined as the number of days from patient enrollment in trial until the date of first neurologic progression or the date of patient's death whichever occurs first, regardless of whether radiological progression has occurred or not. If a patient neither experienced neurologic progression nor died, then the data will be censored at the last date of post-baseline neurologic assessment. If a patient with no post-baseline neurologic assessment did not experience neurologic progression nor died, then the data will be censored at the date of enrollment.

Clinical deterioration free survival (CDFS): CDFS is defined as the number of days from patient enrollment in trial until the date of first clinical deterioration or the date of patient's death whichever occurs first, regardless of whether clinical deterioration has occurred or not. If a patient neither experienced clinical deterioration nor died, then the data will be censored at the last date of post-baseline Karnofsky performance score assessment. If a patient with no post-baseline Karnofsky performance score assessment did not experience clinical deterioration nor died, then the data will be censored at the date of enrollment.

See definitions below.

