7.2.3 Definition of Response and progression

PFS6 is the primary endpoint for Group C. Additionally; several secondary endpoints are based on neuroimaging as assessed by MRI: the response rate, median progression-free survival, and the progression-free survival at defined time points. The sites should base their estimate of response according to the RANO criteria (Ref. 36) which would also be state of the art outside a clinical trial. The subsequent MRIs will be compared to the baseline MRI as defined in Section 7.2.5. In brief, the following definitions apply:

- **Complete Response (CR):** complete disappearance of all enhancing measurable and nonmeasurable disease sustained for at least 4 weeks; no new lesions; stable or improved nonenhancing (T2/FLAIR) lesions; patients must be off corticosteroids (or on physiologic replacement doses only); and stable or improved clinically. Note: Patients with nonmeasurable disease only cannot have a complete response; the best response possible is stable disease.
- **Partial Response (PR):** 50% decrease compared with baseline in the sum of products of perpendicular diameters of all measurable enhancing lesions sustained for at least 4 weeks; no progression of nonmeasurable disease; no new lesions; stable or improved nonenhancing (T2/FLAIR) lesions on same or lower dose of corticosteroids compared with baseline scan; the corticosteroid dose at the time of the scan evaluation should be no greater than the dose at time of baseline scan; and stable or improved clinically. Note: Patients with nonmeasurable disease only cannot have a partial response; the best response possible is stable disease.
- **Stable disease (SD):** does not qualify for complete response, partial response, or progression; stable nonenhancing (T2/FLAIR) lesions on same or lower dose of corticosteroids compared with baseline scan. In the event that the corticosteroid dose was increased for new symptoms and signs without confirmation of disease progression on neuroimaging, and subsequent follow-up imaging shows that this increase in corticosteroids was required because of disease progression, the last scan considered to show stable disease will be the scan obtained when the corticosteroid dose was equivalent to the baseline dose.

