- **Progression (PD):** 25% increase in sum of the products of perpendicular diameters of enhancing lesions compared with the smallest tumor measurement obtained either at baseline (if no decrease) or best response, on stable or increasing doses of corticosteroids; significant increase in T2/FLAIR nonenhancing lesion on stable or increasing doses of corticosteroids compared with baseline scan or best response after initiation of therapy; any new lesion; clear clinical deterioration not attributable to other causes apart from the tumor (e.g., seizures, medication

adverse effects, complications of therapy, cerebrovascular events, infection, and so on) or changes in corticosteroid dose; failure to return for evaluation as a result of death or deteriorating condition; or clear progression of nonmeasurable disease.

The measures previously proposed by RANO (Ref. 36) to measure the clinical deterioration will also be completed and a comparison of both clinical and radiological evaluation will be made.

RANO clinical evaluation will be based on KPS evaluation. Clinical progression is defined as the presence of the following conditions

- a decline in KPS from 100 or 90 to 70 or less, or
- a decline in KPS of at least 20 from 80 or less, or
- a decline in KPS from any baseline to 50 or less, for at least 7 days,

will be considered neurologic deterioration unless attributable to comorbid events or changes in corticosteroid dose.

Criterion	CR	PR	SD	PD
T1 gadolinium enhancing disease	None	$\geq 50\% \downarrow$	$< 50\% \downarrow$ but $< 25\% \uparrow$	$\geq 25\% \uparrow$
T2/FLAIR	Stable or \downarrow	Stable or \downarrow	Stable or \downarrow	\uparrow
New lesion	None	None	None	Present
Corticosteroids	None	Stable or \downarrow	Stable or \downarrow	Not applicable*
Clinical status	Stable or \uparrow	Stable or \uparrow	Stable or \uparrow	\downarrow
Requirements for response	All	All	All	Any

*increase in steroids alone does not qualify for PD

For this trial, the primary measure of response and progression will be determined by the locally assessed response according to the RANO criteria. All treatment decisions should be based on the RANO criteria.

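### NANO, KPS and steroid dose have no scheduled assessment after the end-of-study visit, so Group C NPFS is informatively biased, in a direction that depends on follow-up and on how soon patients worsen

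*Combined protocol and SAP*

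**What the plan says.** The last scheduled NANO, KPS and steroid record is the end-of-study visit (6.3.1), within 30 days (±5) of the last TG02 dose. Under 7.2.5, study treatment is completed at first progression.

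From then on, 6.3.3 lists "Survival, irrespective of type of treatment administered or any progression event". Under the condition "If progression has not occurred" it adds brain MRI, and quality of life in Groups A and B. The Group C table (6.4.3) says that if treatment stops "before progression is observed, brain Gd-MRI should be done every 3 months". After progression, 6.3.3.1 keeps survival, quality of life (A and B) and later antitumour treatment (C). The Group C footnote describes survival contacts "and new anti-tumoral therapy information until death", by visit or telephone. The Follow Up columns for NANO, KPS and steroid dose are empty in 6.4.1, 6.4.2 and 6.4.3.

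Section 7.2.2 ends NPFS at first neurologic progression or the "date of patient's death whichever occurs first, regardless of whether radiological progression has occurred or not". Patients alive without neurologic progression are censored at the last NANO. CDFS is censored in the same way at the last KPS. NPFS and CDFS are Group C secondary endpoints (2.2.2). Section 8.2.2 plans a Kaplan-Meier NPFS6 and median NPFS. For CDFS it plans only a tabulated comparison of event times.

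In 7.2.3, partial response requires that "the corticosteroid dose at the time of the scan evaluation should be no greater than the dose at time of baseline scan". The 25% enhancing-growth and T2/FLAIR progression criteria also refer to steroid dose. Clinical progression is read from KPS and includes "a decline in KPS from any baseline to 50 or less, for at least 7 days".

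**The concern.** NPFS is meant to look past radiological progression, but its measuring instrument is last scheduled about a month after the event that normally ends treatment. Deaths keep being collected at their own dates. Ascertainment of the two components is therefore unequal, and the imbalance depends on how the patient is doing. That is informative observation, and Kaplan-Meier does not correct for it.

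Affected outputs are NPFS6, median NPFS, the PFS/NPFS/CDFS comparison, and the aim of relating NANO to RANO outcome (2.1.2). A KPS fall first seen at the end-of-study visit also has no later scheduled KPS to show that it lasted 7 days.

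A second strand concerns patients who stop before progression. Their 3-monthly scans feed investigator RANO PFS, but the steroid dose and clinical status that several RANO categories need are not scheduled with the scan.

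**Working it through.** **1. The plan's own figures.** No figure is given for NPFS or CDFS. The Group C rule reproduces: with n = 45 and success at 13 or more, P(X ≥ 13 | 0.20) = 0.0995 and P(X ≥ 13 | 0.40) = 0.9554. The one-sided 90% exact lower limit for 13/45 is 0.2002, and 45/0.9 = 50. The point below does not alter this rule.

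**2. Schedule against definitions.**

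| Item | End-of-study visit | Follow-up, not progressed | Follow-up, progressed |
|---|---|---|---|
| Survival | – | yes | yes |
| Brain MRI | yes | yes | no |
| NANO | yes | no | no |
| KPS | yes | no | no |
| Steroid dose | yes | no | no |

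**3. Two opposing effects on NPFS.** Take a patient who stops at radiological progression, is neurologically stable at the end-of-study visit, and worsens 6 weeks after stopping.
- If the patient dies at month 8, recorded NPFS is 8 months. This pushes NPFS up.
- If the patient is alive at the data cut, NPFS is censored at the end-of-study visit, while others' deaths still count at their own dates. This pushes NPFS down.

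**4. Net size.** The simulation used 200,000 patients per setting, the protocol's NANO schedule (every 2 cycles to cycle 6, then every 3), an end-of-study visit 1 month after detected progression, and the 7.2.2 event and censoring rules. From the documents: PFS-6 of 20% or 40% (P0 and P1) and minimum follow-up of 6 months. Assumed: 30–60% have neurologic progression by detected progression; mean lag otherwise 2–24 months; mean survival after progression 3 or 6 months; and the follow-up ranges. Selected results for PFS-6 20% and 30% worsening by detected progression (months; NPFS6 in %):

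| Lag | Survival after progression | Follow-up | 3-monthly NANO | Current schedule | Difference |
|---|---|---|---|---|---|
| 2 | 3 | 12–24 | 37.0 | 40.1 | +3.1 |
| 2 | 6 | 12–24 | 40.9 | 46.6 | +5.7 |
| 12 | 6 | 12–24 | 52.2 | 54.0 | +1.8 |
| 24 | 6 | 12–24 | 54.7 | 55.2 | +0.5 |
| 12 | 6 | 6–12 | 50.5 | 49.7 | −0.8 |
| 24 | 6 | 6–12 | 52.8 | 50.3 | −2.5 |
| 24 | 6 | 6–7 | 42.6 | 37.0 | −5.6 |

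Across all settings with lag 2 months and follow-up of 12 months or more, the current schedule adds about 2 to 6 points at PFS-6 20% (33–47% against 31–41%) and 1 to 4 points at 40% (51–63% against 50–59%). The median moves by 0 to about +1.3 months. In the mature, short-lag settings, 10–27% of patients have neurologic progression between the end-of-study visit and death.

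One result falls outside these ranges. With lag 2, survival 6 and follow-up only 6–7 months, the difference is 33.7 − 21.6 = +12.1 points. There the 3-monthly schedule is a poor benchmark: the model's true value is 35.4%, and many living patients are censored at a last NANO before month 6. Very short follow-up damages NPFS6 under either schedule.

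**5. RANO inputs on follow-up scans.**

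| Criterion | Needs beyond the scan |
|---|---|
| New lesion (progression) | nothing |
| 25% enhancing growth; T2/FLAIR increase | steroid dose |
| Clinical deterioration | KPS or clinical status, steroid change |
| Complete or partial response | steroid dose and clinical status |
| Stable disease | steroid dose; clinical status in the RANO table |

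Only the first row can be completed from what 6.3.3 schedules.

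**The case against.** A reader might infer that NPFS and CDFS are simply biased upward, by around 10 points. A model with no censoring gives that: with PFS-6 20%, a 2-month lag and 4 months from progression to death, true NPFS-6 is 31.6% against 42.0% recorded. The documents do not support it. Section 7.2.2 censors living patients at the last NANO, and no visit schedule observes onset continuously. Under the same lag and survival, 3-monthly NANO gives 36.5%. The current schedule with 7.2.2 censoring gives 35.1% (follow-up 6–7 months) or 37.7% (6–12 months), that is −1.4 or +1.2 points.

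A reader might also infer that RANO status cannot be completed off treatment. That is too strong. A new lesion alone is progression, as is failure to return because of death or deterioration. Sites determine RANO locally. Section 5.4 requires disease assessments after early stopping, 5.6 requires steroid recording with no stated end date, and 7.1.3 asks for a conclusion on neurological status at each evaluation.

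Thirdly, the wording about continuing regardless of radiological progression is written for NPFS only. The corresponding CDFS clause refers to clinical deterioration, its own event, so it is circular and leaves the question open.

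These endpoints are also secondary, descriptive and outside the 13-of-45 rule.

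All of this limits the point without removing it. None of the general duties schedules a NANO or KPS. Appendix I bases NANO on direct examination rather than history, so a missed score cannot be rebuilt from a telephone call or the chart.

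**Conclusion.** The gap between schedule and definition is established from the text. Its consequence is informative bias in Group C NPFS6, median NPFS and the PFS/NPFS/CDFS comparison, not a bias of known sign. Relative to 3-monthly NANO, NPFS6 is roughly 1 to 6 points too high when follow-up is mature and worsening comes soon after progression. It may be up to about 6 points too low when follow-up is short and worsening late. The documents give no rate of neurologic progression or of survival after progression, so these sizes rest wholly on the stated assumptions.

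For CDFS the same loss of KPS applies. It has no planned Kaplan-Meier estimate, and its intended window is unclear until the clause is corrected. For RANO, the inputs are unscheduled rather than unobtainable. The primary PFS-6 count is exposed only through patients who stop treatment before both progression and 6 months; that number cannot be derived from the documents. The point merits an amendment because the fix is cheap and missed examinations cannot be recovered.

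**What to change.** 1. In 6.3.3 and the three summary tables, add NANO, KPS and steroid dose to the 3-monthly pre-progression visit at which MRI is already done. Cost: a few eCRF fields and a few minutes per visit.
2. In 6.3.3.1, for Group C after progression, record NANO and KPS when the contact is in person, and KPS otherwise. KPS by telephone helps CDFS but cannot repair NPFS. Cost: small site workload, with NANO still incomplete where follow-up is remote.
3. In 7.2.2 and 8.2.2, pre-specify a supplementary NPFS and CDFS analysis for deaths more than one scheduled interval after the last NANO or KPS, beside the current definition. Either treat the event as interval-censored between last assessment and death, or show both bounds. Dating it to the last assessment alone would not do: in the uncensored example above that gives about 25.5% against a true 31.6%, while dating at death gives 42.0%. Report the number censored before 6 months alongside. Cost: programming only.
4. Correct the CDFS clause in 7.2.2 to say whether CDFS continues past radiological progression. Cost: one sentence.
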